9.6.1 Statistical Methods for Efficacy Analyses

The analysis of efficacy endpoints will be based on the FAS population. Unless otherwise specified, all efficacy data from participants who have taken at least 1 dose of study intervention will be included in efficacy analyses.

Primary Efficacy Analysis

The LCQ is collected at baseline and after administration of the study intervention at Weeks 6 and 12. The primary efficacy endpoint of this study is the LCQ change from baseline in total score. The primary analysis approach will be conducted utilizing the longitudinal ANCOVA model. In this model, the response vector consists of the LCQ change from baseline in total score at each post-Baseline visit. The model will include factors for intervention group, visit, interaction of treatment by visit, gender, and the baseline LCQ score. The model will use all available LCQ change from baseline in total score at Weeks 6 and 12. Contrasts will be constructed to compare the Gefapixant intervention group to the Placebo group at Week 6 and Week 12. The least squares mean change from baseline with the associated standard errors will be displayed for each intervention group. Overall estimated treatment differences (Gefapixant – Placebo) along with corresponding p-values and 95% CIs will also be presented, with the exception of the primary efficacy endpoint, in which the CI width will be adjusted for an IA (Section 9.6). Further details of the model specification, assumptions, and SAS implementation codes will be provided in the sSAP.

Secondary Efficacy Analysis

The continuous secondary efficacy endpoints will be analyzed using a similar longitudinal ANCOVA model as used for the primary efficacy analysis. The model will include terms for intervention group, visit, interaction of treatment by visit, gender, and baseline score.

Table 4 summarizes the analysis strategy of the primary and secondary efficacy endpoints.

Table 4 Analysis Strategy for Primary and Secondary Efficacy Endpoints

Endpoint/Variable (at Week 12)	Statistical Method	Missing Data Approach
Primary		
Change from baseline in LCQ total score	Longitudinal ANCOVA	Model-based ^a
Secondary		
Change from baseline in Cough Severity VAS score	Longitudinal ANCOVA	Model-based ^a
ANCOVA=analysis of covariance; LCQ=Leicester Cough Questionnaire; VAS=Visual Analog Scale		
^a Includes data collected after early intervention discontinuation.		

The strategy for the IA is described in Section 9.7.

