included in the primary analysis model. The random seed will be set equal to 72644243. This step will generate m monotone-missing datasets.

- 2) Applying parametric regression to the monotone-missing datasets, impute all the missing values. This will be accomplished for each treatment group using “proc mi” within SAS 9.3 or higher utilizing the option “monotone reg”, in conjunction with all of the covariates (excluding treatment) included in the primary analysis model. The random seed will be set equal to 72644243. This step will generate m complete datasets.
- 3) To implement the tipping-point aspect of the procedure, subtract a constant c from each of the imputed values of the active arms (to the detriment of active).
- 4) Analyze each of the post-imputation complete datasets using the primary model, obtaining point estimates for the mean of interest (e.g. change-from-baseline treatment difference at 12 weeks) and the associated variance.

Using “proc mianalyze” within SAS 9.3 or higher, the $m=100$ means and variances from the m analyses will be combined to obtain the final test statistic and p-value (Rubin, 1987). The final test statistic $\bar{Q} / (T^{-1/2})$ is approximately distributed as t_v , where \bar{Q} is the sample mean of the m treatment difference estimates, $T = \bar{U} + (m+1) (B/m)$, \bar{U} is the sample mean of the m variance estimates, and B is the sample variance of the m treatment difference estimates. The degrees of freedom, v , will be computed as follows [Barnard and Rubin, 1999]: $v = [(v_1)^{-1} + (v_2)^{-1}]^{-1}$, where $v_1 = (m-1) [1 + (\bar{U}/(1+m^{-1}) B)]^2$ and $v_2 = (1-\gamma) v_0 (v_0 + 1) / (v_0 + 3)$, with $\gamma = (1+m^{-1}) B / T$ and where v_0 represents the complete-data degrees of freedom .

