3.9 SAMPLE SIZE AND POWER CALCULATIONS

The sample size calculations are powered to test the primary efficacy endpoint, with the following assumptions based on the results from a phase 2 chronic cough study. In MK-7264 Protocol 012, the change from baseline in LCQ total score at Week 12 was 1.1 and 1.7 for 20 mg and 50 mg compared to placebo. In this study, given the population is targeted for participants with recent onset chronic cough (< 12 months) which is different from participants with chronic cough (\geq 12 months) in Protocol 012, conservative assumptions were used for sample size calculation:

- Treatment difference in change from baseline in LCQ total score at Week 12 is 1.1 point
- Common SD of change from baseline in LCQ total score is 3.5

Based on the assumptions above, a total of 414 participants (207 participants per intervention group) will provide at least 80% power. The calculation is based on an overall one-sided $\alpha=0.025$ significance level, adjusted for one IA for efficacy ($\alpha=0.001$), and one final efficacy analysis ($\alpha=0.024$). A dropout rate of 15% at Week 12 is accounted for the sample size calculation to ensure 352 evaluable participants complete the Week 12 evaluation.

With assumptions on the AE rates in the placebo group based on the Protocol 012 results, the minimum detectable AE rate differences are 8.4%, 9.0%, and 7.7% in overall taste-related AEs, oral paresthesia AEs, and oral hypoesthesia AEs, respectively.

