4. APPENDICES

4.1 Model Specification, Assumptions, and Sample SAS Implementation Codes for the Primary Efficacy Analysis

Model

Let Y_{ijt} denote the measurement for subject i , with treatment assignment j , at time t . Here $j = 0, 1$ represent Placebo and MK-7264 45 mg BID, respectively. Also, $t = 0, 1, 2$ represent Baseline, visits at Week 6 and 12, respectively.

The longitudinal ANCOVA model, that is, a mixed linear model will treat percent change from baseline in measurement, $(Y_{ijt} - Y_{ij0})/Y_{ij0}$, as the dependent variable, and adjust for the following independent variables:

- baseline measurement Y_{ij0}
- treatment (categorical variable with 2 levels, Placebo and MK-7264 45 mg BID)
- week (categorical variable with 2 levels, 6, 12)
- Gender (males and females)
- the interaction of treatment by week

Observations across subjects are assumed to be independent. Post-baseline measurements within the same subject are assumed to follow multivariate normal distribution with mean vector as specified above and an unstructured covariance matrix.

This longitudinal model provides valid statistical inference in the presence of possible missing data if the missing data mechanism is ignorable (or more specifically, MAR or MCAR). This missing data mechanism requires that the probability of a data point being missing does not depend on the missing data after adjusting for the observed data.

Reasons for discontinuation from the trial may include lack of efficacy, clinical or laboratory adverse experiences, relocation, withdrawal of consent, protocol deviations, and/or data processing issues. Missing data caused by relocation and data processing issues, are likely to be MCAR. On the other hand, missing data caused by discontinuation due to lack of efficacy may belong to MAR because the discontinuation may depend on the observed efficacy outcomes. The MAR or MNAR mechanisms might each underlie the other reasons to some extent. If treatment in large part determines the loss of data for these other reasons (such as clinical or laboratory adverse experiences), the mechanism may be close to MAR since treatment assignment is an observed variable and included in the analysis model. Based on the prior trial results, missing data due to other reasons is relatively infrequent.

Model Convergence

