If the unstructured covariance matrix fails to converge with the default algorithm, then the AR(1) structure can be used to provide initial values of the covariance parameters.

Example SAS Codes

```
proc mixed data=adeff;
  where avisitn > 0;
  class subjid trt01p avisitn sex;
  model chg = base trt01p avisitn sex trt01p*avisitn/ solution notest;
  repeated avisitn / subject = subjid type=un;
  lsmestimate trt01p*avisitn 'MK at Week 12' [1, 1 2];
  lsmestimate trt01p*avisitn ' Placebo at Week 12' [1, 2 2];
  lsmestimate trt01p*avisitn 'Treatment Differences at Week 12' [1, 1 2] [-1, 2 2];
run;
```

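### The primary model holds the baseline LCQ slope equal at Weeks 6 and 12; if the true slopes differ and baseline-related loss differs by arm, the Week 12 contrast may be biased, and a baseline-by-visit term guards against this at almost no cost

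*Combined protocol and SAP*

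**What the plan says.** Every description of the primary model has the same fixed effects. Protocol 9.6.1 states: "The model will include factors for intervention group, visit, interaction of treatment by visit, gender, and the baseline LCQ score". Protocol 9.1, sSAP 3.1, sSAP 3.6.1 and the variable list in sSAP 4.1 agree, and the example code implements that list: "model chg = base trt01p avisitn sex trt01p*avisitn/ solution notest". The within-subject covariance is unstructured. None of these places has a baseline-by-visit term, and none gives a reason for holding the baseline effect constant over visits.

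On missing data, sSAP 4.1 states: "This longitudinal model provides valid statistical inference in the presence of possible missing data if the missing data mechanism is ignorable". The sentence just before it assumes multivariate normal post-baseline data whose mean vector is the one specified.

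The tipping-point analysis in sSAP 3.6.1 imputes within each arm: "Applying parametric regression to the monotone-missing datasets, impute all the missing values". The jump-to-reference analysis ends with an ANCOVA at the last time point only. Both therefore let the baseline relation at Week 12 differ from that at Week 6.

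**The concern.** Treatment is crossed with visit and the covariance is left free, but the baseline slope is constrained. If that constraint is wrong, the model adjusts the Week 12 means with a slope that does not belong to Week 12. With complete data this is harmless, because randomization balances baseline across the arms. It stops being harmless when those who still have Week 12 data differ in baseline between arms, since the wrong slope then leaves a remainder in the treatment contrast.

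Loss that depends on observed baseline and on arm is still missing at random, so this can happen inside the plan's own assumption. The remainder does not depend on the true treatment effect, so it can also shift the type I error of the primary test. A second consequence is interpretive: a gap between the primary result and the tipping-point result at c = 0 could be read as an effect of missing data when part of it comes from the slope constraint.

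**Working it through.** **Planning figure.** sSAP 3.9 gives: "Treatment difference in change from baseline in LCQ total score at Week 12 is 1.1 point" and "Common SD of change from baseline in LCQ total score is 3.5". With 414 × 0.85 = 351.9, about 176 per arm are evaluable. SE = 3.5 × √(2/176) = 0.373. At the final one-sided 0.024 (critical value 1.977), power = Φ(1.1/0.373 − 1.977) = Φ(0.971) = 83.4%. The stated 80% or more is reproduced.

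**Form of the bias.** Take the response as absolute change, as in the code and the endpoint definition, and suppose all loss occurs after Week 6. Let b6 and b12 be the true baseline slopes, b the fitted common slope, k the regression of the Week 12 residual on the Week 6 residual, and m the mean of centred baseline among those in an arm with Week 12 data. Fitting the model by its Week 6 margin and the conditional distribution of Week 12 given Week 6 yields

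bias in the Week 12 contrast = [(b12 − b) − k(b6 − b)] × (m_gefapixant − m_placebo).

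The first factor is zero if b6 = b12, since then b equals both. The second is zero if loss is unrelated to baseline. If loss is related to baseline in the same way and at the same rate in both arms, the second factor is again zero. Both conditions are needed.

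With similar variances at the two visits, b is near the midpoint and k is near the correlation ρ, so the first factor is about (b12 − b6)(1 + ρ)/2. To first order, m ≈ −(log odds ratio of dropout per baseline SD) × (dropout proportion) × (baseline SD).

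**Assumed inputs (not in the documents).** Baseline SD 3; ρ = 0.6; slopes −0.2 at Week 6 and −0.3 or −0.4 at Week 12; dropout 20% on gefapixant and 10% on placebo, which averages to the planned 15%; dropout odds ratio per SD of 1.5 on gefapixant and 1 or 0.67 on placebo.

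- m_gefapixant = −0.405 × 0.20 × 3 = −0.243.
- m_placebo = 0, or +0.405 × 0.10 × 3 = +0.122. The difference is −0.243 or −0.365.
- Slope gap 0.1: first factor −0.1 × 0.8 = −0.08; bias 0.019 or 0.029.
- Slope gap 0.2: first factor −0.16; bias 0.039 or 0.058.
- Gap 0.2 with odds ratios 2 and 0.5: difference −(0.693 × 0.20 × 3) − (0.693 × 0.10 × 3) = −0.624; bias 0.100.
- Equal slopes: bias 0 whatever the dropout.

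**Check by fitting.** Large-sample maximum-likelihood fits of the specified model and of the model with `base*avisitn`, with correlation 0.6 to 0.7, differed by 0.017 to 0.031 points (gap 0.1), 0.033 to 0.062 (gap 0.2) and 0.08 to 0.11 (gap 0.2, odds ratios 2 and 0.5). With equal slopes the bias was within simulation noise. Placing half the loss before Week 6 reduced the bias somewhat. Swapping the dropout directions reversed its sign.

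**Relative size.** 0.02/1.1 = 2% and 0.06/1.1 = 5.5% of the planning effect.

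**Error rate.** At SE 0.36, one-sided error = 1 − Φ(1.977 − bias/0.36). This gives 0.027 at a bias of 0.02, 0.035 at 0.06 and 0.045 at 0.10, against a nominal 0.024. Simulated trials of 207 per arm with gap 0.2 and odds ratios 1.5 and 0.67 gave 0.032 and 0.040 in two sets of runs for the specified model, against 0.021 and 0.025 with the added term.

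**Cost of the term.** With two post-baseline visits it uses one degree of freedom. When the slopes are truly equal, the mean SE went from 0.3494 to 0.3497 in one run and from 0.3569 to 0.3575 in another. Under much stronger, opposite dropout it went from 0.3591 to 0.3627, a rise of 1.0%.

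**The case against.** Three stronger readings are tempting, and the documents support none of them.

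A reader might infer that the Week 12 contrast is biased whenever baseline-related dropout differs by arm. It is not: with equal slopes at the two visits the bias is zero even under strongly opposite dropout, and nothing in the documents shows that the slopes differ.

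A reader might infer that the validity statement in sSAP 4.1 is false. It follows an assumption that the mean vector is as specified, so it is already conditional on the mean model, as it would be for any parametric model.

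A reader might infer that the added term makes the contrast unbiased in general. With a further treatment-by-baseline slope of ±0.2 at Week 12, the by-visit model still missed by about 0.01 to 0.03 points.

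The dropout story is also assumed. No section says that milder participants leave gefapixant or that sicker ones leave placebo. Stopping treatment is not the same as missing Week 12: data after discontinuation enter the analysis (Table 4 in the protocol, Table 1 in the sSAP), and protocol 8.2.1 encourages continued ePRO completion. Against that, protocol 8.10.3 limits visits after discontinuation to adverse events, concomitant medication and e-Diary assessments, so how much LCQ data will be collected then is unclear.

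Finally, the plan has some protection. The missingness pattern will be inspected, and the tipping-point analysis at c = 0 allows visit-specific slopes. That could reveal a discrepancy, but only as a sensitivity result; the primary test would stand as specified.

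These objections limit the claim to a conditional risk of modest size. They do not supply a reason to keep the constraint.

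**Conclusion.** The point holds as a conditional risk. The constraint is present in all the model descriptions and is unexplained. It can bias the Week 12 contrast only when the baseline slopes differ between visits and baseline-related loss differs by arm; whether either holds cannot be judged from the documents. Under the moderate assumed inputs above the bias is about 0.02 to 0.06 points, less than about one sixth of a standard error (0.06/0.36 = 0.17). It is about 0.1 point in the strong-dropout case. The direction is unknown: the assumed pattern favours gefapixant, and the reverse pattern would make the test conservative. The power calculation is not affected. The change is worth making because it is nearly free and makes the primary contrast safer under the plan's own missing-data assumption, not because an error has been shown.

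**What to change.** Add `base*avisitn` to the MODEL statement in sSAP 4.1. Add a baseline-by-visit interaction to the covariate lists in sSAP 3.1, 3.6.1 and 4.1 and in protocol 9.1 and 9.6.1. Do the same for the Cough Severity VAS model and the CSD model that follow the primary one. WPAI has one post-baseline time point and needs no change.

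The statistical cost is one degree of freedom and an SE change of at most about 1%. The procedural cost is a protocol amendment before any unblinding, because Section 9 of the protocol requires one when methods for the primary hypothesis change. If an amendment is not practicable, name the by-visit model in the sSAP as a prespecified sensitivity analysis of the primary endpoint. In either case, state that the protection rests on a baseline relation that is linear and the same in both arms.

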4.2 Model Specification for the Safety Analysis

Miettinen and Nurminen method

Denote the sample size and response rate as n_0, p_0, n_1, p_1 for the two treatment groups. The $100(1 - \alpha)\%$ confidence interval is provided by solving the equation for δ ,

$$\frac{(\hat{p}_1^* - \hat{p}_0^* - \delta)^2}{\sum_{i=1}^I \left(\frac{w_i}{\sum_k w_k} \right)^2 \tilde{v}_i} = \chi_{1, \alpha}^2$$

Here $i = 1, \dots, I$ is the index for strata and

$$\hat{p}_1^* = \sum_{i=1}^I \left(\frac{w_i}{\sum_k w_k} \right) \hat{p}_{1i}, \text{ where } \hat{p}_{1i} \text{ is the observed response rate for group 1 in stratum } i;$$

$$\hat{p}_0^* = \sum_{i=1}^I \left(\frac{w_i}{\sum_k w_k} \right) \hat{p}_{0i}, \text{ where } \hat{p}_{0i} \text{ is the observed response rate for group 0 in stratum } i;$$

$$w_i = \frac{n_{1i}n_{0i}}{n_{1i}+n_{0i}}, \text{ which corresponds to the Cochran Mantel-Haenszel's weights;}$$

$$\tilde{v}_i = \left[\frac{\tilde{p}_{1i}(1-\tilde{p}_{1i})}{n_{1i}} + \frac{\tilde{p}_{0i}(1-\tilde{p}_{0i})}{n_{0i}} \right] \frac{n_{1i}+n_{0i}}{n_{1i}+n_{0i}-1};$$

\tilde{p}_{0i} is the maximum likelihood estimate for p_{0i} under the restriction that $p_{1i} - p_{0i} = \delta$;

$$\tilde{p}_{1i} = \tilde{p}_{0i} + \delta.$$

The point estimate for the treatment difference is provided by $\hat{p}_1^* - \hat{p}_0^*$ with corresponding variance $\sum_{i=1}^I \left(\frac{w_i}{\sum_k w_k} \right)^2 \tilde{v}_i$.

